7.4.2. Time-To-Event Efficacy Endpoint

The time to achieve Itch NRS score improvement of at least 4 points from baseline (ie, ITCH4) will use the daily Itch NRS score in comparison to baseline Itch NRS score in the DBVC period. A log-rank test will be used for between-treatment group comparisons. The hazard ratio and its 95% CI will be estimated based on the Cox regression model using Efron's method accounting for ties. Kaplan-Meier curves will be presented by treatment groups. The number of participants, number of events, and number of censoring will be summarized by treatment groups. The Kaplan-Meier estimate of median time will be presented with its 95% CI. The 95% CI will be calculated using the method by Brookmeyer and Crowley (1982).

The last available value for time to ITCH4 during the DBVC period is the last nonmissing measurement obtained after the first application of study cream and within 30 days after the last application of study cream in DBVC period, or before the first application of study cream in the OLE period, whichever is earlier.

9. SAFETY AND TOLERABILITY

Appendix A provides a list of data displays.

9.1. General Considerations

The analyses in this section will be provided for the safety population in the DBVC period and OLE evaluable population in the OLE period, unless otherwise specified. Summary tables may be replaced with listings when appropriate. For instance, an AE frequency table may be replaced with a listing if it only contains a few unique preferred terms reported on relatively few participants.

9.2. Adverse Events

9.2.1. Adverse Event Definitions

A TEAE is any AE either reported for the first time or worsening of a pre-existing event after first application of study drug until 30 days of the last application of study drug. For participants who cross over treatments, the first application date is period-specific; however, the end date is 30 days after the last application date in this period, or the first application date in the next period, whichever comes first. Analysis of AEs (as discussed below) will be limited to TEAEs, but data listings will include all AEs regardless of their timing in relation to study drug application. For purposes of analysis, all AEs will be considered TEAEs unless the AE can unequivocally be defined as not treatment-emergent.

Adverse events will be tabulated by MedDRA PT and SOC. Severity of AEs will be graded using the NCI CTCAE v5. The CTCAE reporting guidelines and grading details are available on the Cancer Therapy Evaluation Program website.

The subset of AEs considered by the investigator to be related to study drug will be considered to be treatment-related AEs. If the investigator does not specify the relationship of the AE to study drug, the AE will be considered to be treatment-related. The incidence of AEs and treatment-related AEs will be tabulated. In addition, serious TEAEs will also be tabulated.

Any missing onset date, causality, or severity must be queried for resolution. Unresolved missing causality and severity will be handled according to the following rules:

- An unresolved missing causality will be considered treatment-related.
- An unresolved missing severity will be identified as an unknown severity.

Any missing onset date of a TEAE will be handled according the following rules:

- If completely missing, then Day 1 will be used.
- If only the day is missing, then the first day of the month or Day 1, whichever is later, will be used.
- If both the month and day are missing, then 01 JAN of the year or Day 1, whichever is later, will be used.

For purposes of analysis, all AEs will be considered TEAEs unless the AE can unequivocally be defined as not treatment-emergent.

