Because LS carries a serious long-term risk of cancerous transformation with a cumulative incidence of vulvar SCC of 6.7% (Bleeker et al 2016), usually treatment for LS is lifelong with close follow-up to detect early signs of vulvar carcinoma. Once the symptoms are well-controlled after an initial intensive treatment with high-potency steroids, participants are recommended to use maintenance therapy in which they apply topical steroids from 2 times a week to once a day. For this reason, this trial will include an OLE period for maintenance treatment. Participants will be asked to continue treatment without stopping unless there are AEs that necessitate treatment discontinuation. The use of ruxolitinib cream during the OLE period will demonstrate continued safety and efficacy of ruxolitinib 1.5% cream in LS.

This study will evaluate the efficacy and safety of ruxolitinib 1.5% cream BID versus vehicle in LS. The VC period is 12 weeks. Participants who are randomly assigned to ruxolitinib 1.5% cream will continue to treat (ruxolitinib 1.5% cream QD) active LS areas during the OLE for additional 12 weeks. Participants assigned to vehicle will then be crossed over to receive active maintenance treatment for an additional 12 weeks. During the OLE period, all participants will apply ruxolitinib 1.5% cream through Week 24 at least once per day. Participants who develop symptoms or signs of active disease during OLE period on ruxolitinib 1.5% cream QD treatment regimen will have dose increased to ruxolitinib 1.5% cream BID until symptoms and signs have resolved. At the Week 12 visit, the LS treatment area will be evaluated by the investigator to assess for symptoms and signs of active disease. Those participants who in the opinion of the

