4.2. Overall Study Duration

The study begins when the first participant signs the study ICF. It is estimated that an individual will participate for approximately 32 weeks, including up to 28 days for screening, 12 weeks for treatment during the DBVC period, 12 weeks for treatment during the OLE period, and up to 30 days for follow-up after the last application of study treatment. If a biopsy is done to confirm the diagnosis of LS during screening period, screening period can be extended to 6 weeks to allow for histological examination.

The end of the study is defined as the date of the last visit of the last participant in the study. A participant is considered to have completed the study if they have completed all study visits including the safety follow-up visit.

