9.2.2. Adverse Event Summaries

An overall summary of AEs by treatment group will include the following:

- Number (%) of participants reporting any TEAEs
- Number (%) of participants reporting any serious TEAEs
- Number (%) of participants reporting any Grade 3 or higher TEAEs
- Number (%) of participants reporting any treatment-related TEAEs
- Number (%) of participants who temporarily interrupted study treatment because of TEAEs
- Number (%) of participants who permanently discontinued study treatment because of TEAEs
- Number (%) of participants who had any fatal TEAEs

The following summaries will be produced by MedDRA term (if 2 or fewer participants appear in a table, a listing may be appropriate):

- Summary of TEAEs by MedDRA SOC and PT
- Summary of TEAEs by MedDRA PT in decreasing order of frequency
- Summary of TEAEs by MedDRA SOC, PT, and maximum severity
- Summary of TEAEs by MedDRA SOC, PT, and CTCAE grade category
- Summary of Grade 3 or higher TEAEs by MedDRA SOC and PT
- Summary of Grade 3 or higher TEAEs by MedDRA PT in decreasing order of frequency
- Summary of serious TEAEs by MedDRA SOC and PT
- Summary of serious TEAEs by MedDRA PT in decreasing order of frequency
- Summary of treatment-related TEAEs by MedDRA SOC and PT
- Summary of treatment-related TEAEs by MedDRA PT in decreasing order of frequency
- Summary of Grade 3 or higher treatment-related TEAEs by MedDRA SOC and PT
- Summary of treatment-related serious TEAEs by MedDRA SOC and PT
- Summary of TEAEs with a fatal outcome by MedDRA SOC and PT
- Summary of TEAEs leading to dose interruption by MedDRA SOC and PT
- Summary of TEAEs leading to discontinuation of study drug by MedDRA SOC and PT
- Summary of Application Site Reactions by MedDRA PT in decreasing order of frequency

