3.2.16.x	Summary of Treatment-Emergent Adverse Events Leading to Discontinuation of Study Drug by MedDRA System Organ Class and Preferred Term	Safety	X
3.2.17.x	Summary of Application Site Reactions by MedDRA Preferred Term in Decreasing Order of Frequency	Safety	X
3.3 Labora	tory		
3.3.1.1.x	Summary of Laboratory Values – Hematology	Safety	X
3.3.1.2.x	Summary of Laboratory Values – Chemistry	Safety	X
3.3.2.1.x	Shift Summary of Hematology Laboratory Values – to the Worst Abnormal Value	Safety	X
3.3.2.2.x	Shift Summary of Chemistry Laboratory Values – to the Worst Abnormal Value	Safety	X
3.3.3.1x	Shift Summary of Hematology Laboratory Values in CTCAE Grade – to the Worst Grade Abnormal Value	Safety	X
3.3.3.2.x	Shift Summary of Chemistry Laboratory Values in CTCAE Grade – to the Worst Grade Abnormal Value	Safety	X
3.4 Vital Si	gns		
3.4.1.x	Summary of Systolic Blood Pressure	Safety	X
3.4.2.x	Summary of Diastolic Blood Pressure	Safety	X
3.4.3.x	Summary of Pulse	Safety	X
3.4.4.x	Summary of Respiratory Rate	Safety	X
3.4.5.x	Summary of Body Temperature	Safety	X

Note: For AE tables ending with "x," separate tables will be provided for the DBVC period, OLE period, and the treatment periods (ie, DBVC and OLE periods). For laboratory and vital sign tables ending with "x," separate tables will be provided for the DBVC and the OLE periods.

Figures

Figure No.	Title	Population
Efficacy		
4.1.1.1	Proportion of Participants Achieving ITCH4 in Treatment Periods	ITT
4.1.1.2	Proportion of Participants Achieving ITCH4 by Baseline ITCH NRS Score in Treatment Periods	ITT
4.1.1.3	Proportion of Participants Achieving ITCH4 by Baseline IGA Score in Treatment Periods	ITT
4.1.1.4	Proportion of Participants Achieving ITCH4 by Baseline Age Group in Treatment Periods	ITT
4.1.1.5	Proportion of Participants Achieving ITCH4 by Baseline Duration of Disease in Treatment Periods	ITT
4.1.1.6	Proportion of Participants Achieving ITCH4 by Pre and Postmenopausal Status in Treatment Periods	ITT
4.1.1.7	Forest Plot of Response Rate Difference in Achieving ITCH4 at Week 12	ITT
4.1.2.1	Mean and Standard Error Plot of By-Visit Itch NRS Score in Treatment Periods	ITT
4.1.2.2	Mean and Standard Error Plot of Change From Baseline in By-Visit Itch NRS Score in Treatment Periods	ITT

Figure No.	Title	Population
4.1.3.1	Mean and Standard Error Plot of Daily Itch NRS Score From Day 1 to Day 28	ITT

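### A woman who completes both periods has about 84 days of adverse event window in the DBVC tables and about 114 in the OLE tables, so the crude percentages are not comparable between periods

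*SAP*

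**What the plan says.** SAP 9.2.1 defines a TEAE in general as an event that is new or worsens "after first application of study drug until 30 days of the last application of study drug". For participants who cross over treatments it makes the start date period-specific and sets the end of the window thus: "the end date is 30 days after the last application date in this period, or the first application date in the next period, whichever comes" earlier.

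SAP 9.2.2 summarises events as counts and percentages of participants, for example "Number (%) of participants reporting any TEAEs". The note to the safety tables in SAP Appendix A says that for AE tables "separate tables will be provided for the DBVC period, OLE period, and the treatment periods (ie, DBVC and OLE periods"). Neither section plans a rate per person-time. SAP 6.4 summarises duration of treatment by period, but counts only the days from first to last application.

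On the purpose of the extension, Protocol 2.1.1 says: "The use of ruxolitinib cream during the OLE period will demonstrate continued safety and efficacy of ruxolitinib 1.5% cream in LS". Protocol 6.1 starts the OLE at the Week 12 visit, so no gap between periods is planned.

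**The concern.** The two treatment periods are equally long, but their event windows are not. For a woman who continues, the DBVC window shuts when OLE dosing begins, so it contains no post-treatment time. Her OLE window runs on for 30 days after the last application. A percentage of participants with an event depends on how long they were watched, and these tables do not show that the watching time differs.

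Because the OLE is meant to show continued safety, readers will set its percentages beside those of the DBVC period. The vehicle-to-ruxolitinib group is the clearest case: the same women contribute about 84 days on vehicle, then about 114 days on or after active drug. An unchanged event rate could be read as an increase on active drug, and a real fall in rate could be masked.

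**Working it through.** **Inputs.** Protocol 4.2 gives "12 weeks for treatment during the DBVC period, 12 weeks for treatment during the OLE period, and up to 30 days for follow-up", that is 84, 84 and up to 30 days. It also says "an individual will participate for approximately 32 weeks, including up to 28 days for screening". The window rule is in SAP 9.2.1. The documents give no AE rate for lichen sclerosus, so the incidences below are assumptions.

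**The plan's own figure.** 28 + 84 + 84 + 30 = 226 days; 226 / 7 = 32.3 weeks, against about 32 stated. The period lengths are therefore read correctly.

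**Windows for a woman who enters and completes the OLE.** The end of a window is the earlier of (last application in the period + 30 days) and (first application in the next period).

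- DBVC: about 84 days (81 to 87 with the ±3-day visit window).
- OLE: 84 + 30 = 114 days (108 to 120 with both visit windows).
- Ratio: 114 / 84 = 1.36. Share of the OLE window that is off treatment: 30 / 114 = 26%.

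A DBVC completer who does not enter the OLE keeps the 30-day tail and has 114 days in the DBVC table.

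**Effect on a crude percentage.** Let p be the DBVC incidence and λ = −ln(1 − p) / 84 the daily hazard. OLE incidence is 1 − exp(−λ × T), where T is the effective number of days at the DBVC hazard:

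- same hazard throughout: T = 114
- half the hazard in follow-up: T = 84 + 15 = 99
- no events in follow-up: T = 84
- whole OLE window at 0.70 of the DBVC hazard: T = 0.70 × 114 = 79.8

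| Assumed DBVC | Same hazard | Half in follow-up | Zero in follow-up | OLE hazard × 0.70 |
|---|---|---|---|---|
| 20% | 26.1% | 23.1% | 20.0% | 19.1% |
| 30% | 38.4% | 34.3% | 30.0% | 28.7% |
| 50% | 61.0% | 55.8% | 50.0% | 48.2% |

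The crude OLE figure exceeds the DBVC figure only if the mean hazard over the OLE window is above 84 / 114 = 0.74 of the DBVC hazard.

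**Does a person-time rate repair it?** Only if time is censored at the first event. Expected person-time per woman is then (1 − exp(−λT)) / λ, so the rate returns λ whatever the window length. For p = 30%, λ = 0.3567 / 84 = 0.00425 per day, or 155 per 100 person-years in both periods. Dividing by the full window does not work: at p = 50%, 0.50 / 84 = 0.00595 and 0.610 / 114 = 0.00535, about 10% lower in the OLE with no change in hazard.

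**Combined DBVC and OLE tables.** If the continuing ruxolitinib group has one unbroken window, it has 84 + 84 + 30 = 198 days on or after active drug, against 114 for vehicle-to-ruxolitinib.

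**The case against.** A reader might infer that OLE incidence is higher by construction. The documents do not support that. Observation time is longer by construction; incidence is not. There are reasons for a lower OLE hazard: entry is limited to protocol-compliant women with no safety concern, application may be once daily, the last 30 days are off drug, and an event must be new or worse to count. This stands, and is why the table includes the zero-hazard and lower-hazard columns.

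A reader might also infer that the randomized comparison is distorted. One rule governs both arms in the DBVC period, so there is no bias by design. Unequal dropout could change the mix of risk time, but not in a fixed direction: a woman who stops at Week 4 has 28 + 30 = 58 days, fewer than 84, and only stopping after about day 54 gives a longer window. No differential dropout is documented.

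The period-specific sentence is worded for those who cross over. Protocol 4.1 uses that term for the vehicle group and says that the ruxolitinib group continues. For the latter, the 84/114 split is inferred from the separate period tables; the definition of Day 1 by period in SAP 4.1.1 points the same way. This limit stands and is itself something to settle.

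No formal comparison between periods is planned, and counts with percentages are usual in a small Phase 2 trial. With about 30 women per arm, 30% against 38.4% is 9 women against 11.5, and the standard error of 30% is √(0.3 × 0.7 / 30) = 8.4 points. Listings carry all events whatever their timing, so post-treatment events could be picked out by hand. These points limit the weight of the concern, but do not make the tables comparable. The table shells are in a separate document and could not be checked.

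**Conclusion.** The concern holds as a matter of comparability. For women who enter and complete the OLE, the window is about 84 days in one set of tables and 114 in the other, and the planned statistic does not account for it. At an equal constant hazard the OLE percentage would be higher: 30% would read about 38%. The difference shrinks to nothing if no events occur in follow-up, and reverses if the OLE hazard falls below about 0.74 of the DBVC hazard. These sizes rest on assumed incidences and a constant-hazard model. The 84 and 114 days rest on the SAP rule, read directly for the vehicle-to-ruxolitinib group and by inference for the continuing group. Neither the primary efficacy result nor the randomized DBVC safety comparison is affected by design. The issue is how the extension's safety tables can be read against the stated aim of showing continued safety.

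**What to change.** - In SAP 9.2.1, state that the period-specific window applies to both groups, including women who continue on ruxolitinib.
- In SAP 9.2.2, tabulate OLE TEAEs with onset up to the last OLE application, and show the 30-day post-treatment events separately.
- For the overall, serious and treatment-related summaries, by period and for the combined DBVC and OLE tables, add exposure-adjusted incidence: participants with a first event per 100 person-years, with person-time censored at that event and on-treatment time kept apart from follow-up time. This split also deals with women who stop in the DBVC period or complete it without entering the OLE.
- Keep the crude percentages alongside.

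The cost is SAP wording, derived risk-time variables and a few extra table columns. The necessary dates are already to be recorded: last application (Protocol 7.1.2), AE start and end (Protocol 9.3), and treatment duration by period (SAP 6.4). Trial conduct does not change. The rates assume a roughly constant hazard, which separating on-treatment from follow-up time makes easier to defend.

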9.2.2. Adverse Event Summaries

An overall summary of AEs by treatment group will include the following:

- Number (%) of participants reporting any TEAEs
- Number (%) of participants reporting any serious TEAEs
- Number (%) of participants reporting any Grade 3 or higher TEAEs
- Number (%) of participants reporting any treatment-related TEAEs
- Number (%) of participants who temporarily interrupted study treatment because of TEAEs
- Number (%) of participants who permanently discontinued study treatment because of TEAEs
- Number (%) of participants who had any fatal TEAEs

The following summaries will be produced by MedDRA term (if 2 or fewer participants appear in a table, a listing may be appropriate):

- Summary of TEAEs by MedDRA SOC and PT
- Summary of TEAEs by MedDRA PT in decreasing order of frequency
- Summary of TEAEs by MedDRA SOC, PT, and maximum severity
- Summary of TEAEs by MedDRA SOC, PT, and CTCAE grade category
- Summary of Grade 3 or higher TEAEs by MedDRA SOC and PT
- Summary of Grade 3 or higher TEAEs by MedDRA PT in decreasing order of frequency
- Summary of serious TEAEs by MedDRA SOC and PT
- Summary of serious TEAEs by MedDRA PT in decreasing order of frequency
- Summary of treatment-related TEAEs by MedDRA SOC and PT
- Summary of treatment-related TEAEs by MedDRA PT in decreasing order of frequency
- Summary of Grade 3 or higher treatment-related TEAEs by MedDRA SOC and PT
- Summary of treatment-related serious TEAEs by MedDRA SOC and PT
- Summary of TEAEs with a fatal outcome by MedDRA SOC and PT
- Summary of TEAEs leading to dose interruption by MedDRA SOC and PT
- Summary of TEAEs leading to discontinuation of study drug by MedDRA SOC and PT
- Summary of Application Site Reactions by MedDRA PT in decreasing order of frequency

9.3. Clinical Laboratory Tests

9.3.1. Laboratory Value Definitions

All laboratory assessments will be performed using a central laboratory with the exception of urine pregnancy tests. Laboratory values and change from baseline values will be summarized descriptively by visit; non-numeric test values will be tabulated when necessary. Baseline will be determined according to Section 4.1.3, using the last nonmissing value collected before the first application, prioritizing scheduled assessments for baseline identification over unscheduled visits. The last record before application in the highest priority will be considered the baseline record. For baseline laboratory candidates with the same date and time in the same priority category, additional rules may be provided after consultation with the medical monitor to delineate which value will be defined as baseline.

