| LS assessment under magnification* | X | X | X | X | X | X | X | X | X | | | *See Section 8.3.4.3. |
| Vital signs | X | X | X | X | X | X | X | X | X | X | X | |
| AE assessments | X | X | X | X | X | X | X | X | X | X | X | |
| Efficacy assessments | | | | | | | | | | | | |
| | | | | | | | | | | | | |
| CLISSCO | X | X | X | X | X | X | X | X | X | | | |
| | ı | | | | | | 1 | | 1 | 1 | | |
| %BSA* | X | X | X | X | X | X | X | X | Х | X | | *The total %BSA affected should be ≤ 10% to be eligible for study entry and continued participation. |
| Photography (selected sites only) | | X | | X | X | X | X | X | X | | | |

Table 3: Schedule of Activities (Continued)

| | | | | | | | | | | | Safety | |
|---------------------------|-----------|-----------|-----------|-------------|-------------|--------------|-----------|-----------|---------------------------------|----------------|----------------------------|--|
| | Screening | | | DBV | C Perio | | | OLE Pe | eriod ^a | | Follow-up | |
| | Days | Baseline | | | | | | | Wk 24 (EOT2)/ET ^b | | 30 Days (+ 7 Days After | |
| Visit Day (Range) | −28 to −1 | (Day 1) | (± 3 d) | $(\pm 3 d)$ | $(\pm 3 d)$ | (± 3 d) | (± 3 d) | (± 3 d) | (± 3 d) | Visit | Last Application) | Notes |
| Patient-reported outco | omes | | | | | | | | | | | |
| | | | | | | | | | | | | |
| Itch NRS | | Completed | l each ev | ening th | rough th | e last appli | cation of | study dru | ıg. | | | |
| Skin Pain NRS | | Completed | l each ev | ening th | rough th | e last appli | cation of | study dru | ıg. | | | |
| Laboratory assessmen | nts. | | | | | | | | | | | |
| | î . | X* | | 1 | 1 | X | | 1 | X | Χ [†] | X | *N-4 |
| Chemistry assessments | X | X | | | | X | | | X | Χ' | | *Not necessary if screening assessment is performed within 14 days of Day 1. |
| | | | | | | | | | | | | †Laboratory assessment are optional during unscheduled visits based on investigator's discretion and clinical judgment. |
| Hematology assessments | X | X* | | | | X | | | X | Χ [†] | | *Not necessary if screening assessment is performed within 14 days of Day 1. |
| | | | | | | | | | | | | †Laboratory assessment are optional during unscheduled visits based on investigator's discretion and clinical judgment. |

Table 3: Schedule of Activities (Continued)

| | Screening | | | DBV | C Period | Į | | OLE Pe | rioda | | Safety Follow-up | |

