8.1.2. Screening Procedures

Screening is the interval between signing the ICF and the day the participant is enrolled in the study (Day 1). Screening may not exceed 28 days. Assessments that are required to demonstrate eligibility may be performed over the course of 1 or more days during the screening process.

Procedures conducted as part of the participant's routine clinical management (eg, blood counts or physical examinations) and obtained before signing of the ICF may be used for screening or baseline purposes provided that the procedure meets the Protocol-defined criteria and has been performed in the timeframe of the study (ie, within 28 days or less prior to Day 1). For participants who are enrolled in the study, information associated with eligibility requirements must be entered into the appropriate eCRF pages.

Results from the screening visit evaluations will be reviewed to confirm eligibility before randomization and the administration of study drug. Tests with results that fail eligibility requirements may be repeated once during screening if the investigator believes the results to be in error. For screening assessments that are repeated, the most recent available result before randomization will be used to determine eligibility.

See Sections 5.4 and 5.5 for information regarding screen failures and replacement of participants, respectively.

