4.1.3. Baseline Value

Baseline is the last nonmissing measurement obtained before or on the day of the first application of ruxolitinib cream or vehicle cream for the DBVC period.

For randomized participants not treated with any study treatment, baseline is defined as the last nonmissing assessment before or on the date of randomization.

For participants who continue in the OLE period, baseline is defined as follows:

- For efficacy evaluation in the OLE period, baseline is the last nonmissing measurement obtained before or on the day of first application of study treatment in the DBVC period.
- For safety evaluation in the OLE period, baseline is the last nonmissing measurement obtained before or on the day of first application of ruxolitinib 1.5% cream in the study.

When a scheduled assessment and an unscheduled assessment occur on the same day and the times of the assessments are not available, use the following convention to determine baseline:

- If both a scheduled and an unscheduled visit are available on the day of the first application and the time is missing, use the scheduled assessment as baseline.
- If the scheduled assessment is missing on the day of the first application and an unscheduled assessment is available, use the unscheduled assessment as baseline.

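### SAP 9.3.1 ranks scheduled laboratory records above later unscheduled ones, contrary to SAP 4.1.3, so a superseded value can become the safety baseline

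*SAP*

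**What the plan says.** SAP 4.1.3 gives the general rule: "Baseline is the last nonmissing measurement obtained before or on the day of the first application of ruxolitinib cream or vehicle cream". Its preference for a scheduled over an unscheduled assessment is a tie-break. It applies only when both fall on the same day and their times are not available.

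SAP 9.3.1 starts from that rule: "Baseline will be determined according to Section 4.1.3, using the last nonmissing value collected before the first application". It then sets its own order, with no mention of a shared date, by "prioritizing scheduled assessments for baseline identification over unscheduled visits. The last record before application in the highest priority will be considered the baseline record". Its next sentence deals with records that match on date and time within one priority category. That confirms the order: category first, date second.

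Two Protocol provisions decide when this matters. Section 8.1.2 lets a failing screening test be repeated once if the investigator thinks the result is in error, and adds: "For screening assessments that are repeated, the most recent available result before randomization will be used to determine eligibility". The Schedule of Activities (Table 3) plans chemistry and hematology at both screening and Day 1, but notes on the Day 1 draw: "Not necessary if screening assessment is performed within 14 days of Day 1".

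**The concern.** The two SAP sections give different baselines for the same participant, although one claims to follow the other. A programmer working from 4.1.3 takes the newest pre-dose value. A programmer working from the last part of 9.3.1 takes the newest scheduled value, even if a later unscheduled one exists.

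The awkward case is a participant whose scheduled screening result failed, whose repeat was acceptable, and who had no Day 1 draw. If the repeat is recorded as unscheduled, 9.3.1 keeps as baseline the value that the investigator believed wrong and passes over the one that supported enrollment.

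This baseline feeds the change-from-baseline summaries, the low/normal/high shift table, the CTCAE grade shift table and the count of participants whose abnormalities worsened (SAP 9.3.1 and 9.3.2). Safety is a stated objective, and SAP 3.3 calls the sample size sufficient to evaluate the safety profile.

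**Working it through.** This is a derivation rule, so the plan has no figure to reproduce. The check applies both rules to the same records.

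**Rules.**
- 4.1.3: baseline is the latest value up to Day 1; if a scheduled and an unscheduled record share that date without times, take the scheduled one.
- 9.3.1, read literally: if any scheduled pre-dose value exists, baseline is the latest scheduled value; otherwise it is the latest unscheduled value.

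**Formula.** Change = on-treatment value − baseline. Where the rules differ, change under 9.3.1 minus change under 4.1.3 = later unscheduled value − older scheduled value.

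**Inputs.** The hemoglobin exclusion limit of < 100 g/L is from Protocol 5.2. The individual values are assumptions: failing 98, repeat 125, Day 1 124 where drawn (taken as pre-dose), on-treatment 98 g/L. In case E the later value is set at 100, because a result below 100 would exclude the participant.

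| Case | Pre-dose records | 4.1.3: baseline, change | 9.3.1: baseline, change |
|---|---|---|---|
| A | Scheduled Day −20: 98; unscheduled Day −15: 125; scheduled Day 1: 124 | 124, 98 − 124 = −26 | 124, −26 |
| B | Scheduled Day −12: 98; unscheduled Day −6: 125; Day 1 waived | 125, 98 − 125 = −27 | 98, 98 − 98 = 0 |
| C | As B, repeat filed under the screening visit | 125, −27 | 125, −27 |
| D | Scheduled Day −20: 98; unscheduled Day −10: 125; Day 1 waived on the strength of the repeat | 125, −27 | 98, 0 |
| E | Scheduled Day −12: 125; unscheduled Day −6: 100; Day 1 waived | 100, 98 − 100 = −2 | 125, 98 − 125 = −27 |

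The rules agree in A and C. In B and D, 9.3.1 removes a fall of 27 g/L (125 − 98 = 27). In E it adds a fall of 25 g/L that 4.1.3 does not show (100 − 125 = −25).

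**Effect on a shift table.** Take ALT, with an exclusion limit of > 2.5 × ULN (Protocol 5.2). Assume scheduled 2.8 × ULN on Day −13, unscheduled repeat 1.0 × ULN on Day −6, Day 1 waived, and Week 12 at 2.8 × ULN. Under 9.3.1 the change is 2.8 − 2.8 = 0 and the row is high to high. Under 4.1.3 it is 2.8 − 1.0 = +1.8 × ULN and the row is normal to high.

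SAP 9.3.2 uses the baseline category as denominator, so one reassigned participant alters two rows. With about 60/2 = 30 per arm, suppose all 30 are normal under 4.1.3 and only this participant becomes high. The normal-to-high entry is 1/30 = 3.3%. Under 9.3.1 it is 0/29, and a baseline-high row of 1/1 appears.

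**The case against.** The strongest objection is that the path is narrow. A reader might infer that everyone who enters on a repeat carries the failing value as baseline. The documents do not support that, because two further conditions are needed.

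First, there must be no Day 1 draw. Those labs are scheduled and are waived only within the 14-day limit. Participants who stop topical LS treatment at the screening visit need a 2-week washout (Protocol 5.1 and 5.2), so their screening labs will often be at or past that limit. This stands. It does not close the path, since not everyone needs that washout, Protocol 8.1.2 allows screening assessments on more than one day, and a draw can be missed.

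Second, the repeat must be recorded as unscheduled. Protocol 8.1.2 speaks of screening assessments that are repeated, and Protocol 8.6 describes unscheduled visits as medically warranted ones. A repeat may well be filed under screening, in which case the last scheduled record is the normal repeat (case C). Neither document settles the coding. Case D also has to treat the repeat as a screening assessment for the waiver but as unscheduled for baseline.

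A reader might also infer that worsening is hidden. That is too strong. Post-baseline values by visit, the overall counts of low and high values and the abnormal-value listings still show the on-treatment result. Clinically meaningful abnormalities are reported as adverse events (Protocol 9.1), and the distortion can run the other way (case E). Protocol 10.4.3 plans no formal group comparison of laboratory data.

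These points limit the consequence. They do not remove the contradiction between the two SAP sections.

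**Conclusion.** The point holds as an inconsistency in the SAP with a conditional effect. The literal ordering in 9.3.1 conflicts with the section it cites. It can select a superseded baseline when Day 1 labs are waived or missing and the latest pre-dose result is coded as unscheduled.

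For each such participant, the recorded change is off by the difference between the two pre-dose values: 27 g/L or 1.8 × ULN in the assumed examples, in either direction. One participant is 3.3% of an arm of about 30.

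The number affected cannot be estimated from the documents. It is zero if repeats are always filed under screening or Day 1 labs are always drawn. A reader might put a rate on it. For example, assuming that 2% to 10% of 60 enter after a repeat gives 1.2 to 6 people. That range has no basis in the documents, and it counts participants with repeats, not those who also meet both conditions. Full rescreening under Protocol 5.4 brings a new participant number, so the point concerns single-test repeats and other unscheduled pre-dose results.

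The primary efficacy result is not touched. The open-label extension adds little. Vehicle participants have scheduled Week 12 labs that must be completed before entry, and participants already on ruxolitinib keep their pre-Day 1 baseline under SAP 4.1.3. The correction should be made, but no conclusion of the trial depends on it.

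**What to change.** In SAP 9.3.1, confine the scheduled-over-unscheduled preference to records on the same date without times, as in 4.1.3. State that laboratory baseline is the most recent nonmissing pre-dose result, including a repeated screening test, whether it is coded as scheduled or unscheduled. The rest of 9.3.1 can stay, including consultation with the medical monitor over exact ties.

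The cost is about two sentences of SAP text and one line of derivation code. No extra data, visits or site work are needed.
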